4.3 Power Calculation

The goal of the study is to compare the differences in the CSF, blood and saliva levels of CD44 between 1) the control group and the Optune alone and the TMZ + Optune group; and 2) Optune alone vs, TMZ + Optune alone.

There is no previous literature on CD44 levels in GBM. To calculate a sample size, we are assuming that the baseline and post treatment levels of CD44 standard form in the CSF will be approximately 327 ± 134 ng/ml and 185 ± 103 , respectively, similar to those reported by Kawano et al. for head and neck cancer(12). One of the drawbacks of the report is that they only reported the median and do not specify if it is the standard deviation or range that they reported.

For the primary goal, it is assumed that the median is similar to the mean and the reported value is the standard deviation. Further assumptions are: sample sizes of n=10 and n=20 (for the control and the cancer groups, respectively); significance level of 0.05; expected means of 327 and 185 (for the cancer and the control groups, respectively); common standard deviation of 115; independence of the sample units and normality of the observations. The power was calculated using a two sample t-test and it was found to be 87%. Power calculation was performed with PASS v.13.0.4.

4.4 Data Analysis.

Descriptive statistics will be provided. Categorical data will be reported as count (percentages). Continuous data will be reported as mean (standard deviation) or median (range) as appropriate. A two sample t-test will be used to compare the biomarker level between groups, unless the distributions are found to be non-symmetric. In that case, Wilcoxon-Rank-Sum tests will be used.

5. Human Subjects

Thirty individuals will take part in this study at Baylor Scott & White Healthcare. Body fluids we requested are considered to have concern of human subject.

Risks (including physical, emotional, social, and/or privacy)

Risks of Radiation – Diagnostic Test: Patients will have the same amount of radiation exposure regardless of whether the participant elects to take part in this research study or receives standard medical care.

Risks of participation in the study for individuals using Optune alone or Optune plus TMZ: TMZ is commonly used to treat patients with GBM. Common side effects of patients using TMZ include nausea, vomiting, loss of appetite, constipation, diarrhea, skin rash, tiredness, weakness, dizziness, blurred vision, sleep problems (insomnia), unusual or unpleasant taste in your mouth, and headache. Optune is a FDA approved device for GBM patients as well. In a large clinical study, patients who received Optune for at least 18 hours a day responded better to treatment. Because Optune works differently, it does not cause many of the side effects associated with chemotherapy. The most common side effect reported is skin irritation occurring under the transducer array. These reactions go away shortly after the TMZ and/or Optune are stopped. We are studying possible risks and reactions related to the TMZ and Optune. Current studies show that both TMZ and Optune are very safe to be used for GBM patients and no risk related to the use of TMZ and/or Optune has been reported so far.

Risks of blood and CSF withdrawals: Withdrawal of CSF (5 ml), blood (2 ml), and saliva (5 ml) from patients is a standard practice in the hospital. In general we do not expect more than a minor risk for patients. However, patients after withdrawal of CSF may have back pain for short time, or bleeding (this only happens to the patients with bleeding disorder and these subjects are excluded from the study) or infection. The incidence of having infection is very rare as the procedure will be very clean. In the case of back pain, patients will receive pain killer such as nonsteroidal anti-inflammatory drugs (NSAIDs), or Ibuprofen to stop pain. In the case of infection, patients will receive antibiotics.

Risks of Genetic Testing: In this study, only a few genes will be tested and this test will only help doctors understand that certain therapies are better for a particular subset of patients. The results will NOT show whether the disease is caused by genetic abnormalities or linked to a particular patient. Thus patient and patient's family members will not face any problems in obtaining insurance coverage. However, in case there is possible any kind of risk to patients, or patient's family members, to keep this from happening,

the results of this test will NOT be given to anyone outside the study staff. This means that the results will not be made available to patients, patients' family members, patients' private physician, patients' employer, patients' insurance company, and/or any other party unless required by law.

Use of Genomic Testing Information: In this study, the samples will only be used for the specific regions related potential biomarkers for GBM; the results from this test will not include the full genomic information about any patient. This information from this test should NOT affect patients' insurance coverage. Insurance companies in Texas may not use the results of genetic testing to deny anyone insurance coverage, cancel their coverage, or increase their premiums. Even so, to avoid any potential risk, we will do everything possible to make sure that the results of genomic testing are not given to anyone except the study staff. The results of the testing will not be given to patients or patients' family, will not be placed in patients' medical record, and will not be given to patients' private physician, patients' employer, patients' insurance company, and/or any other party unless required by law. To further protect against the misuse of this information, patients' name will be removed from the results before the results are shared with the sponsor of the study.

Risks of Genomic Testing: The genomic tests in this study will not show that patient's disease is caused by genetic abnormalities; patients' family members will not face problems in obtaining insurance coverage for this disease. However, to keep this from happening, the results of this test will NOT be given to anyone outside the study staff. This means that these results will not be made available to the patients, patients' family members, patients' private physician, patients' employer, patients' insurance company or any other party unless required by law.

Benefits to the Subjects (if none, indicate none)

There will be no benefit to the subjects for participating in this study but future patients may benefit from this study.

Informed Consent (indicate how it will be obtained, who will obtain it, and how it will be documented; if not practicable, justify why it is not and how forgoing consent will not adversely impact the subjects' rights and welfare, included their right to the privacy of their medical records)

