The **objective** of this proposed study is to determine the expression levels of a panel of markers including CD133, CD44, ABCC3, TNFRSF1A, AKT1, IDH2, and MGMT in GBM tissues and the CSF, blood, and saliva from patients with GBM receiving different types of treatment as described in Figure 1 and the non-brain tumor patients (controls). Our aims are: 1) To compare the differences of CD44 between the control group and the combined cancer groups at baseline; and 2) To compare the levels of CD44 and other markers among the 3 different groups such as control vs. GBM patients and Optune vs. Optune + TMZ after 8 weeks of treatment. Exploratory analysis of all other markers will be performed.

Figure 1 Overall strategy

4. Methodology

4.1 Study Design.

To reach our goal, a small clinical study will be performed with the support from NovoCure Inc. In this study, 30 participants will be enrolled in which 10 non-brain tumor patients (e.g., patients will have other types of minor neurological disorder(s) that necessitate a lumbar puncture e.g., headache, epilepsy or neurodegenerative disorders such as Alzheimer's disease or Multiple sclerosis or Parkinson's disease) will be used as the control. As shown in Figure 1, 20 patients (n=20) with GBM will be divided into two groups; patients in group 3 will receive the combination of TMZ (150-200 mg/m² orally every day; 5 consecutive days per 28-day treatment cycle for 6 cycles) with Optune and patients in group 2 will receive Optune only. (The GBM patients will be monitored for tumor size using MRI and CT scan before and after each type of treatment, which is standard of care for all GBM patients.) We will collect the CSF (5 ml), blood (2 ml), and saliva (5 ml) from each participant as indicated in Figure 2 before and after treatment (Optune alone or Optune plus TMZ for detection of biomarkers. These samples will be used for detection of selected biomarkers at gene (RNA and DNA) and protein levels. CSF is standard of care for all GBM patients, we will ask to store the leftover tumor tissues for our research.

4.2 Subject Selection/Participants.

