The participants in both non-brain tumor group and GBM groups (male and/or female, there is no preference at this time) should be over 22 years old without pregnancy, or an infectious disease (cold, flu, HIV, etc.) or a blood disorder (e.g., lack of platelets, anemia, thrombosis) or vascular malformations. For controls, only patients evaluated for the neurological disorders whose evaluation required spinal taps at both the Neurology clinic and the Brain Tumor clinics will be used for this study. This is an exploratory pilot study. Based on others previous experiences, 30 subjects (10 subjects in each group) will allow us to estimate the levels of selected biomarkers in the body fluids of different groups of patients and the potential value of these selected biomarkers for GBM prognosis.

4.3 Procedures/Methods.

For the non-brain tumor control group, 5 ml of CSF, 2 ml of blood, and 5 ml of saliva will be collected one time from each participant. For the GBM patients, patients will first receive surgery to remove the tumor (the tissue will be used for diagnosis and we will use the left over for the biomarker detection) followed by radiation and/or chemotherapy according to patients' health conditions. (CSF are standard of care for these patients.) Thereafter, the physician will discuss with the patients and help patients pick their FDA approved treatment options to receive Optune or Optune plus TMZ.

All of the GBM patients will be asked for blood, saliva, and CSF withdraws at three time points as indicated in Figure 2 (the first time point is at after surgery +/- 1 week and before the combination of radiation and chemotherapy; the second time point is immediately before starting Optune/TMZ treatment +/- 3 days [at 6 weeks after the combination treatment]; and the third time point is at 8 months after the Optune/TMZ treatment +/- 1 month). The samples collected will be used to determine the levels of selected potential biomarkers at protein, DNA/RNA levels. These data will be used to assess the efficacy of the treatments for GBM patients and the correlation of the efficacies of the treatments with the expression levels of testing biomarkers in their CSF, blood, and saliva.

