The control group will have no interaction with anything as they will not receive any anticancer treatment and all participants without brain tumor will be signed up in this group.

Data collection variables

The time points for data and sample collection will follow the schedule as indicated in Figure 2. The first point will be served as the baseline; the second point will be the intermediate; and the third point will be the endpoint for the biomarker study of using CSF samples. The data generated from the patients' samples will be kept in the lab. As these data do not contain any privacy information, there will be no privacy concern.

The data for the tumor sizes and patients' general performs will be a part of the standard care. Data collection forms can be Excel spreadsheets or created in Microsoft Access (the Data Management group can create these for the PI).

For privacy concerns, all the information about participants from this study will only be shown to the people working on the study. The results of this study may be published in a scientific book or journal. If this is done, the name of any participants will not be used. All information about participants from this research project will be kept in a locked office. Information that is kept on computers will be kept safe from access by people who should not see it. Sensitive information is not allowed to transfer or distribute to the third party without permission. All investigators who deal with collected tissue samples on this application have taken or will take the respective institutional "human subject protection" training for this project. Only Key Study Personnel (KSP) will have access to collected data and that it will be housed in secure environment. The data will not be destroyed at least for 6 year.

Tumor tissues will be collected from patients for diagnosis and future research e.g., evaluating the levels of biomarkers selected. The tissues will be snap-frozen (fresh-frozen, FF) and then stored at -80 or liquid nitrogen. Alternatively, it could be formalin-fixed paraffin-embedded (FFPE) for long time storage (10 years). All samples are expected to be used for diagnosis, thus, though the original samples may be labeled with patients' information. However, the patients' information will not be released to the researchers. The pathologist will change the label to GBM with numbers only.

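### Optune v Optune + TMZ: patients and physicians choose the arm, but the planned test is unadjusted and ignores the level drawn just before treatment

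*Protocol*

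**What the plan says.** - **Arm allocation (Protocol, 4.3 Procedures/Methods).** After surgery, then radiation and/or chemotherapy depending on health, "the physician will discuss with the patients and help patients pick their FDA approved treatment options to receive Optune or Optune plus TMZ". No randomisation, matching or stratification is described.
- **Aim (section 3).** The second aim includes "Optune vs. Optune + TMZ after 8 weeks of treatment". Section 4.3 Power Calculation restates this contrast as the second goal.
- **Test (4.4 Data Analysis).** "A two sample t-test will be used to compare the biomarker level between groups, unless the distributions are found to be non-symmetric"; otherwise a Wilcoxon rank-sum test. No covariate or change score is mentioned.
- **Samples (4.3 Procedures/Methods).** GBM patients are sampled three times. The first draw follows surgery and precedes radiation and chemotherapy; "the second time point is immediately before starting Optune/TMZ treatment"; and "the third time point is at 8 months after the Optune/TMZ treatment".
- **Labels (Data collection variables).** "The first point will be served as the baseline; the second point will be the intermediate". The third draw is the endpoint.
- **Intended use (4.3 Procedures/Methods).** "These data will be used to assess the efficacy of the treatments for GBM patients".

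**The concern.** Where health and preference steer treatment, the two arms may differ in CD44 before Optune/TMZ begins. An unadjusted comparison of post-treatment levels cannot separate that difference from anything the treatments do. The protocol says it will use these data to judge efficacy, so the misreading is a real risk.

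The value that would reduce the problem is already collected at the second draw. The protocol calls that draw only intermediate and gives the baseline label to the post-surgery draw. An analyst who adjusted for the protocol's baseline would use a level that precedes radiation and chemotherapy, not the level at which the arms diverge.

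**Working it through.** **The plan's own figure.** Inputs from 4.3 Power Calculation: means 327 and 185 ng/ml (difference 142), SD 115, n = 20 and 10, alpha 0.05 (taken as two-sided). Noncentrality = 142 / (115 × √(1/10 + 1/20)) = 3.19 on 28 df, giving power 86.8%. The stated 87% reproduces. It concerns control v combined GBM only; the protocol gives no power for Optune v Optune + TMZ.

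**Assumptions for the second aim.** 10 v 10, two-sided 0.05, normal data, SD 115 ng/ml before and after. Not in the protocol, so varied or borrowed: the correlation r between the second-draw and post-treatment levels (0 to 0.7); the gap D between arms at the second draw (0.5 SD = 57.5 ng/ml); and, for power only, the 142 ng/ml difference from the other comparison. ANCOVA results, and the rates in the bias table, come from simulating 200,000 trials per setting.

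**Bias with no treatment effect.**

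(a) The arms differ only through the measured level. The expected post-treatment gap is r × D. The t-test is biased by that amount; ANCOVA is unbiased.

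(b) The gap is a stable arm difference, D at both times. The t-test is biased by D and ANCOVA by D × (1 − r).

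The t-test's noncentrality is bias in SD / √(2/10) on 18 df. For example, in (a) at r = 0.5, 0.25 / 0.447 = 0.56 gives 8.3%.

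| D = 0.5 SD | r = 0 | 0.3 | 0.5 | 0.7 |
|---|---|---|---|---|
| (a) t-test bias, ng/ml | 0 | 17 | 29 | 40 |
| (a) t-test false positives | 5.0% | 6.3% | 8.3% | 11.5% |
| (a) ANCOVA false positives | 5.0% | 5.0% | 5.0% | 4.9% |
| (b) t-test bias, ng/ml | 58 | 58 | 58 | 58 |
| (b) t-test false positives | 18.5% | 18.5% | 18.5% | 18.5% |
| (b) ANCOVA bias, ng/ml | 58 | 40 | 29 | 17 |
| (b) ANCOVA false positives | 16.9% | 11.4% | 8.9% | 7.0% |

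With D = 1 SD in (a), t-test false positives are 9.7%, 18.5% and 31.7% at r = 0.3, 0.5 and 0.7. The rank-sum test behaves similarly (8.3%, 16.2%, 27.9%), so the fallback gives no protection.

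**Power for 142 ng/ml.** The t-test's noncentrality is 142 / (115 × √0.2) = 2.76 on 18 df, giving 74.3%.

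| Power | r = 0 | 0.3 | 0.5 | 0.7 |
|---|---|---|---|---|
| ANCOVA, arms balanced | 71.7% | 75.5% | 83.1% | 94.1% |
| ANCOVA, arms 0.5 SD apart | 68.9% | 72.9% | 80.6% | 92.5% |

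Break-even with balanced arms: ANCOVA multiplies the variance by (1 − r²) × (1 + 1/16), which equals 1 at r = √(1/17) = 0.24. Simulated power at r = 0.25 is 74.1%, in agreement.

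**The case against.** - **This could be left to the statistical analysis plan.** Section 4.4 is short and generic, and covariates are often specified later. But it names a test and the quantity tested, which is a choice and not a silence. The mention in section 4.1 of sampling before and after treatment describes collection, not analysis.
- **ANCOVA is not the only remedy.** In (b) a change-score t-test holds 5% at every r. In (a) it gives about 12%, 10%, 8% and 7% at r = 0, 0.3, 0.5 and 0.7. Neither method dominates, and neither removes confounding by fitness or tumour status. This stands. It argues for stating the assumption and showing both, not for leaving the comparison unadjusted.
- **Chance imbalance is no argument.** Two randomly formed arms of 10 differ by at least 0.5 SD with probability 2 × (1 − Φ(0.5/√0.2)) = 26%, but under random allocation the t-test still holds 5%. This is correct. The 26% shows only that such a gap is not extreme; the bias comes from choice of arm.
- **The size is assumed.** It is. At r = 0.3 in (a) the false-positive rate is only about 6%, and at r = 0 it is 5%.
- **Missing draws cost power.** If two patients per arm lacked the second draw, ANCOVA at 8 v 8 would have 60%, 64%, 72% and 87% power at r = 0, 0.3, 0.5 and 0.7, against 74% for the t-test at 10 v 10. This stands as a practical caution.
- **It is an exploratory pilot and a second aim.** This is true and limits the weight of the point.

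**Conclusion.** The concern holds. The protocol fixes an unadjusted comparison of levels for arms formed by choice and gives the draw taken just before treatment no role in it. Under the assumed 0.5 SD gap, adjustment removes the bias if the gap acts through the measured level and reduces it, for r above zero, if the gap is stable. Precision improves only for r above about 0.25. Adjustment cannot make the contrast evidence of efficacy, because other reasons for choosing an arm remain. The change should be made but is modest: the aim is secondary, the study is an exploratory pilot, and the 87% power for the primary comparison is unaffected.

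**What to change.** In section 4.4, for Optune v Optune + TMZ only (controls are sampled once):

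1. Analyse post-treatment CD44 by ANCOVA with group and the second-draw level as covariate, on the log scale if skewed. Report the adjusted difference with a 95% confidence interval.
2. State that the covariate is the second draw, not the post-surgery draw labelled baseline.
3. Show the change-score and unadjusted comparisons as supporting analyses, with the number of patients who have both draws.
4. Describe the result as a non-randomised, exploratory association with residual confounding, and align the efficacy wording in 4.3 Procedures/Methods.
5. Reconcile the 8 weeks in section 3 with the 8 months in 4.3 Procedures/Methods, so that the outcome sample is defined.

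The cost is wording and one degree of freedom; no new sample or visit is needed. If r is zero, power falls from 74.3% to 71.7% with balanced arms, or to 68.9% with arms 0.5 SD apart. Missing second draws would add to that loss.
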